## 4.4 Early study termination

The study can be terminated at any time for any reason by Novartis. Reasons for early termination:

- Unexpected, significant, or unacceptable safety risk to participants enrolled in the study
- Decision based on recommendations from applicable board(s) after review of safety and efficacy data
- Discontinuation of study drug development

In taking the decision to terminate, Novartis will always consider participant welfare and safety. Should this be necessary, the participant should be seen as soon as possible and the same assessments should be performed as described in [Section 7.1.4](#) for a discontinued or withdrawn participant. The investigator may be informed of additional procedures to be followed in order to ensure that adequate consideration is given to the protection of the participant's interests. The investigator or sponsor depending on local regulation will be responsible for informing IRBs and/or ECs of the early termination of the trial.

## 5 Population

### 5.1 Study population

For the Phase Ib and the Phase II Group 1 (EGFRmut, any T790M, any MET, 2/4L antineoplastic, EGFR TKI resistant), Group 3 (EGFRmut, T790M negative, any MET, 1L antineoplastic), and Group 4 (EGFRmut, any T790M, any MET, 1L (treatment naïve) 2-3L antineoplastic), adult participants with advanced or metastatic EGFR mutant L858R and/or ex19del NSCLC will be eligible (or other rare activating mutations that confer sensitivity to first and second generation EGFR inhibitors (e.g. L861Q, G719X, S768I)), whereas for Phase II Group 2 participants harboring a de novo EGFRT790M mutation will be eligible to participate in this study.

During the Phase Ib dose escalation part, participants who have progressed on first or second generation EGFR TKI treatment (e.g. gefitinib, erlotinib or afatinib) will be enrolled.

The Phase II Group 1 (EGFRmut, any T790M, any MET, 2/4L antineoplastic, EGFR TKI resistant) will enroll participants who had a clinical benefit (complete response (CR)/PR any duration or stable disease (SD) for at least 6 months) on first or second generation EGFR TKI and subsequently progressed on this first or second generation EGFR TKI treatment. Participants should not have received more than one prior line of EGFR TKI and no more than three prior lines (including the EGFR TKI) of antineoplastic therapy for NSCLC. Participants in the Phase II part Group 1 (EGFRmut, any T790M, any MET, 2/4L antineoplastic, EGFR TKI resistant) will be assigned according to their acquired resistance mechanism to four sub-groups:

- a. sub-group 1a : EGFRmutL858R/ex19del NSCLC with acquired mutation T790M (*T790M+*, *MET dysregulation-*)
- b. sub-group 1b : EGFRmutL858R/ex19del NSCLC with demonstrated MET dysregulation (*T790M-*, *MET dysregulation+*). MET dysregulation is defined as either MET gene copy number  $\geq 4$  by FISH and/or IHC 3+ (defined as  $\geq 50\%$  of cells staining with high intensity).

- c. sub-group 1c: EGFRmutL858R/ex19del NSCLC with evidence of both acquired T790M and MET dysregulation (*T790M+*, *MET dysregulation+*)
- d. sub-group 1d: EGFRmutL858R/ex19del NSCLC with MET below the levels for sub-group b (*T790M-*, *MET dysregulation-*).

In the Phase II part Group 2 (EGFRmut, de novo T790M, any MET, 1/3L antineoplastic, EGFR TKI naïve), participants should not have received prior EGFR inhibitor treatment and no more than two prior lines of antineoplastic therapy for NSCLC.

In the Phase II Group 3 (EGFRmut, T790M negative, any MET, 1L antineoplastic), participants should not have received any prior line of systemic antineoplastic therapy in the advanced setting (NSCLC stage IIIB or IV). However, participants who have received no more than 1 cycle of systemic antineoplastic therapy in the advanced setting are allowed.

In the Phase II Group 4 (EGFRmut, any T790M, any MET, 1L (treatment naïve) 2-3L antineoplastic) participants, with documented EGFRmut NSCLC, who have never received any systemic antineoplastic therapy or have failed (defined as intolerance to treatment or documented disease progression) a maximum of 2 lines of antineoplastic therapies for advanced disease will be enrolled. Group 4 participants will take study drugs with food (unrestricted meal type).

In the Phase II Group 5 (EGFRmut, T790M-, MET GCN  $\geq 5$ , 2L, EGFR TKI resistant), previously documented EGFR activating mutation (e.g., L858R and/or ex19del), T790M negative, MET amplified who have progressed on one prior line of therapy EGFR TKI for advanced/metastatic NSCLC disease will be given capmatinib monotherapy followed by capmatinib in combination with nazartinib.

The investigator or designee must ensure that only participants who meet all the following inclusion and none of the exclusion criteria are offered treatment in the study.

## 5.2 Inclusion criteria

Participants eligible for inclusion in this study have to meet **all** of the following criteria:

1. Written informed consent must be obtained prior to any screening procedures.
2. Participants (male or female)  $\geq 18$  years of age.
3. Participants in Phase Ib and Phase II Groups 1 to 4 with histologically documented, locally advanced or recurrent (stage IIIB who are not eligible for combined modality treatment) or metastatic (Stage IV) non-small cell lung cancer.  
Participants in Phase II Group 5 must have stage IIIB/IIIC (not amenable to curative surgery, chemoradiation or radiation) or stage IV NSCLC at the time of study entry according to AJCC version 8.
4. Participants in Phase Ib and Phase II Groups 1 to 4 must have advanced NSCLC with locally documented EGFRL858R mutation and/or ex19del (or other rare activating mutations that confer sensitivity to first and second generation EGFR inhibitors (e.g. L861Q, G719X, S768I), or a characterized de novo EGFRT790M mutation).  
Biomarker requirements for participants in Phase II Group 5 are detailed in Inclusion criteria 15.
5. Presence of at least one measurable lesion according to RECIST 1.1 as per [Appendix 1](#).

6. ECOG performance status  $\leq 1$
7. Participants must be screened for HBV. Participants who are either HBsAg positive or HBV-DNA positive must be willing and able to take antiviral therapy 1-2 weeks prior to first dose of study treatment (capmatinib+nazartinib) and continue on antiviral therapy for at least 4 weeks after the last dose of study treatment. Additional management of the participants would be provided by a physician with expertise in management of HBV, if needed.
8. Participants must be screened for HCV. Participants must have negative hepatitis C antibody (HCV Ab) or are HCV Ab positive but with an undetectable level of HCV-RNA. Note: participants with detectable HCV-RNA are not eligible for the study.
9. **For Phase Ib**, participants must have either an acceptable local result detailing their MET and EGFRT790M status in a biopsy collected at or post progression on the previous EGFR TKI therapy, or sufficient tumor material available from a biopsy collected at or post progression on prior EGFR TKI for central assessment of MET and EGFRT790M. **For Phase II**, participants must have sufficient material available for results from central assessment of MET and EGFRT790M. The biopsy must be collected at or post progression on last EGFR TKI treatment line for Group 1 (EGFRmut, any T790M, any MET, 2/4L antineoplastic, EGFR TKI resistant) and Group 5 (EGFRmut, T790M-, MET GCN $\geq 5$ , 2L, EGFR TKI resistant), at any time for Group 2 (EGFRmut, de novo T790M, any MET, 1/3L antineoplastic, EGFR TKI naïve), Group 3 (EGFRmut, T790M negative, any MET, 1L antineoplastic) and Group 4 (EGFRmut, any T790M, any MET, 1L (treatment naïve) 2-3L antineoplastic).
10. **Phase Ib only**: documented progression of disease according to RECIST 1.1 while on continuous treatment with EGFR TKI (e.g. erlotinib, gefitinib or afatinib).
11. **Phase II Group 1 (EGFRmut, any T790M, any MET, 2/4L antineoplastic, EGFR TKI resistant) only**: Participants demonstrated a documented clinical benefit (CR (any duration), PR (any duration), or SD for at least 6 months) on prior EGFR TKI (e.g. erlotinib, gefitinib or afatinib) and subsequently demonstrated progression according to RECIST 1.1.
12. **Phase II Group 2 (EGFRmut, de novo T790M, any MET, 1/3L antineoplastic, EGFR TKI naïve) only**: Participants must have advanced NSCLC with a “de novo” T790M EGFR mutation:
  - a. Participants must have NSCLC harboring a documented EGFRT790M mutation identified by the Novartis designated central laboratory. An archival or newly obtained tumor sample must be available for molecular pre-screening.
  - b. For purposes of this protocol “de novo” T790M will be defined as the presence of EGFRT790M in NSCLC participants who have NOT been previously treated with any therapy known to inhibit EGFR.
13. **Phase II Group 3 (EGFRmut, T790M negative, any MET, 1L antineoplastic) only**: participants must harbor an EGFR activating mutation and must be naïve from any line of systemic antineoplastic therapy in the advanced setting.
14. **Phase II Group 4 (EGFRmut, any T790M, any MET, 1L (treatment naïve) 2-3L antineoplastic) only**: All participants must harbor an EGFR activating mutation and 2/3L participants must have failed (defined as intolerance to treatment or documented disease progression) a maximum of 2 prior lines of antineoplastic therapy in the advanced setting.

**15. Phase II Group 5 (EGFRmut, T790M-, MET GCN $\geq$ 5, 2L, EGFR TKI resistant) only:**

- Histologically or cytologically confirmed diagnosis of NSCLC (excluding squamous cell carcinoma) with all the following:
  - EGFR mutations known to be associated with EGFR TKI sensitivity. This must be assessed as part of the participant standard of care by a validated test for EGFR mutations, as per local regulations. Exon 19 del, L858R, either alone or in combination with other EGFR sensitivity mutation assessed by a CLIA-certified USA laboratory or an accredited local laboratory outside the USA must be documented in the participant source documents before the participant can be consented for pre-screening for MET amplification status.
  - EGFR T790M negative status for participants who have progressed on first or second generation EGFR TKI, or third generation EGFR TKI other than osimertinib, as per tissue-based result from a CLIA-certified USA laboratory or an accredited local laboratory outside of the USA, by a validated test according to local regulations. Results must be documented in the participant source documents before the participant can be consented for pre-screening for MET amplification. If a local T790M result is not available, T790M status in tissue per central Novartis-designated laboratory result is required.
  - MET gene amplification defined as: Gene copy number (GCN)  $\geq$  5 per tissue-based result from a CLIA-certified USA laboratory or an accredited local laboratory outside of the USA by a test that is validated according to local regulations with results documented in the participant source documents. An adequate amount of tumor tissue (archived or if not available, newly obtained biopsy sample) must be available at the time of enrollment for central assessment of MET gene amplification status. If a local result is not available, a tumor tissue sample must be submitted and determined as MET amplified (GCN  $\geq$  5) per central Novartis-designated laboratory.
  - Histological transformation from NSCLC into small cell lung cancer (SCLC) following previous EGFR TKI treatment are excluded.
- Participants must have progressed on one prior line of therapy either to first/second generation EGFR TKIs, osimertinib or other third generation EGFR TKIs for advanced/metastatic disease (stage IIIB/IIIC [not amenable to curative surgery, chemoradiation or radiation or stage IV NSCLC). Acquired resistance to EGFR TKI treatment is defined as documented clinical benefit (CR [any duration], PR [any duration], or SD for at least 6 months) on prior first/ second EGFR TKIs (e.g., erlotinib, gefitinib, afatinib, dacomitinib), osimertinib or other third generation EGFR TKI (such as almonertinib and furmonertinib) and subsequently demonstrated radiological disease progression. Maintenance therapy given after first line chemotherapy will be considered as part of the first line if given to participants with documented response or stable disease before starting the maintenance therapy. Neo-adjuvant and adjuvant systemic chemotherapies will count as one prior line of treatment if relapse occurred within 12 months from the end of the neo-adjuvant or adjuvant systemic therapy. Adjuvant osimertinib therapy will count as prior line of EGFR TKI treatment if relapse occurs during the adjuvant osimertinib therapy.

16. Participants must have a life expectancy of at least 3 months.
17. Willing and able to comply with scheduled visits, treatment plan and laboratory tests.

### 5.3 Exclusion criteria

Participants eligible for this study must not meet **any** of the following criteria:

#### 1. Phase Ib:

- More than one previous treatment line with erlotinib, gefitinib or afatinib
- Previous treatment with any investigational agent known to inhibit EGFR (mutant or wild-type)
- Participants who have received more than three prior lines of antineoplastic therapies (including EGFR TKI) in advanced setting.

#### 2. Phase II:

- Group 1 (EGFRmut, any T790M, any MET, 2/4L antineoplastic, EGFR TKI resistant):
  - More than three prior lines of systemic antineoplastic therapies (including EGFR TKI) in the advanced setting
  - More than one previous treatment line with first or second generation EGFR TKI (e.g. erlotinib, gefitinib, afatinib) in the advanced setting
  - Previous treatment with an investigational or marketed third generation EGFR TKI (e.g. osimertinib, CO-1686, nazartinib)
  - Previous treatment with other investigational or marketed agent known to inhibit EGFR (e.g. EGF monoclonal antibody therapy, dual TKI inhibitor)
- Group 2 (EGFRmut, de novo T790M, any MET, 1/3L antineoplastic, EGFR TKI naïve):
  - More than two previous treatment lines of systemic antineoplastic therapies in the advanced setting.
  - Previous treatment with an investigational or marketed agent that inhibits EGFR. EGFR inhibitors include (but not limited to) all generations of EGFR TKI (e.g. erlotinib, gefitinib, afatinib, osimertinib, CO-1686, nazartinib) or other anti-EGFR or EGFR monoclonal antibody therapy or dual TKI inhibitors.
- Group 3 (EGFRmut, T790M negative, any MET, 1L antineoplastic):
  - De novo EGFR T790M mutation identified by central assessment
  - Previous treatment with any systemic antineoplastic therapy in the advanced setting (NSCLC stage IIIB or IV). Participants who received only one cycle of systemic antineoplastic therapy in the advanced setting are allowed.
- Group 4 (EGFRmut, any T790M, any MET, 1L (treatment naïve) 2-3L antineoplastic):
  - More than two prior lines of systemic antineoplastic therapies in the advanced setting
  - Previous treatment with an investigational or marketed third generation EGFR TKI (e.g. osimertinib, CO-1686, nazartinib)
  - Previous treatment with an investigational or marketed agent that inhibits EGFR (e.g.: EGF monoclonal antibody therapy or dual TKI inhibitors).

For participants in Group 1 to 4, systemic antineoplastic therapy administered as adjuvant or neo-adjuvant treatment more than six months prior to study enrollment is not considered a prior line of therapy for purpose of this study. For participants in Group 5, please refer to inclusion criteria 15.

3. Previous treatment with a MET inhibitor or HGF-targeting therapy.

4. Participants with symptomatic brain metastases. However, participants with asymptomatic/controlled brain metastases may participate in the trial. If treatment is required, these participants must have completed any planned radiation therapy and/or surgery > 2 weeks prior to the first dose of study treatment and remain asymptomatic. Participants must be neurologically stable, having no new neurologic deficits on clinical examination, and no new findings on central nervous system imaging. Participants taking steroids must have been on a stable dose for two weeks prior to the first dose of study treatment.

For Group 5: Participants with symptomatic CNS metastases who are neurologically unstable or have required increasing doses of steroids within the 2 weeks prior to study entry to manage CNS symptoms. If participants are on corticosteroids for endocrine deficiencies or tumor-associated symptoms other than CNS related, dose must have been stabilized (or decreasing) for at least 5 days before Cycle 1 Day 1.

5. Any medical condition that would, in the investigator's judgment, prevent the participant's participation in the clinical study due to safety concerns or compliance with clinical study procedures (e.g., active infection, inflammation, intestinal obstruction, unable to swallow medication, social/psychological issues, etc.). Any severe, acute, or chronic medical or psychiatric condition or laboratory abnormality or substance abuse that may increase the risk associated with study participation or study treatment administration or that may interfere with the interpretation of study results and, in the judgment of the investigator, would make the participant inappropriate for the study.

6. Presence or history of another malignancy.

Exception: Participants who have been disease-free for 3 years, or participants with a history of adequately treated in-situ carcinoma of the uterine cervix, completely resected basal or squamous cell carcinoma, non-melanomatous cancer of skin, history of stage IA melanoma that has been cured, are eligible.

For Group 5: Presence or history of a malignant disease other than NSCLC that has been diagnosed and/or required therapy within the past 3 years. Exceptions to this exclusion include completely resected basal cell and squamous cell skin cancers, and completely resected carcinoma in situ of any type.

7. Undergone a bone marrow or solid organ transplant.

8. Known history of human immunodeficiency virus (HIV) seropositivity (HIV testing is not mandatory).

For Group 5: Participants with known history of testing positive for human immunodeficiency virus (HIV) infection, and with a history of acquired immunodeficiency syndrome (AIDS)-defining opportunistic infections in the last 12 months prior to the first dose of study treatment must be excluded. HIV participants at high risk or with history of uncontrolled opportunistic infection must also be excluded. HIV participants coinfecting with hepatitis virus must also be excluded. To ensure that effective anti retroviral treatment (ART) is tolerated and that toxicities

are not confused with investigational drug toxicities, trial participants should be on established ART for at least four weeks prior to enrollment, they should have the disease under control and suppressed viral loads defined as per local guideline.

9. Participants receiving concomitant immunosuppressive agents or chronic corticosteroids use at the time of study entry except for control of brain metastases, topical applications, inhaled sprays, eye drops or local injections.
10. Participants with clinically significant, uncontrolled cardiovascular disease, such as:
  - Unstable angina within 6 months prior to screening
  - Myocardial infarction within 6 months prior to screening
  - Participants with a history of documented congestive heart failure (New York Heart Association functional classification III-IV)
  - Participants with uncontrolled hypertension defined as a Systolic Blood Pressure (SBP)  $\geq 160$  mm Hg and/or Diastolic Blood Pressure (DBP)  $\geq 100$  mm Hg, with or without anti-hypertensive medication. Initiation or adjustment of antihypertensive medication(s) is allowed prior to screening
  - Ventricular arrhythmias
  - Supraventricular and nodal arrhythmias not controlled with medication
  - Other cardiac arrhythmia not controlled with medication
  - Participants with corrected QT (QTc)  $\geq 470$  ms using Fridericia correction (QTcF) on the screening ECG (using the average QTcF of the triplicate ECGs)
11. Presence or history of interstitial lung disease or interstitial pneumonitis, including clinically significant radiation pneumonitis (i.e., affecting activities of daily living or requiring therapeutic intervention).
12. Unable or unwilling to swallow tablets or capsules.
13. Participants have received anti-cancer therapies within the following time frames prior to the first dose of study treatment:
  - Conventional cytotoxic chemotherapy:  $\leq 4$  weeks ( $\leq 6$  weeks for nitrosoureas and mitomycin-C)
  - Biologic therapy (e.g., antibodies):  $\leq 4$  weeks
  - Non-cytotoxic small molecule therapeutics:  $\leq 5$  half-lives (if half-life known) or  $\leq 2$  weeks
  - Other investigational agents:  $\leq 4$  weeks
  - For Group 5: Previous anti-cancer and investigational agents within 4 weeks or  $\leq 5$  x half-life of the agent (whichever is shorter) before first dose of capmatinib. If previous treatment is a monoclonal antibody, then the treatment must be discontinued at least 4 weeks before first dose of capmatinib. If previous treatment is an oral targeted agent, then the treatment must be discontinued at least 5 x half-life of the agent.
  - For Group 5: Treatment with a prior first or second generation EGFR TKIs (e.g., erlotinib, gefitinib, afatinib, dacomitinib), osimertinib or another third generation EGFR TKIs within 14 days or approximately 5x half-life, whichever is shorter, of the first dose of study treatment (if sufficient washout time has not occurred due to schedule or PK properties, an alternative appropriate washout time based on known duration and

time to reversibility of drug related adverse events could be agreed upon by Novartis and the Investigator).

14. Participants who have received thoracic radiotherapy to lung fields  $\leq 4$  weeks prior to starting the study treatment or participants who have not recovered from radiotherapy-related toxicities. For all other anatomic sites (including radiotherapy to thoracic vertebrae and ribs), radiotherapy  $\leq 2$  weeks prior to starting the study treatment or participants who have not recovered from radiotherapy-related toxicities. Palliative radiotherapy for bone lesions  $\leq 2$  weeks prior to starting study treatment.
15. Major surgery:  $\leq 2$  weeks.  
For Group 5: Major surgery (e.g., intra-thoracic, intra-abdominal or intra-pelvic) within 4 weeks prior (2 weeks for resection of brain metastases) to starting capmatinib or who have not recovered from side effects of such procedure. Video-assisted thoracic surgery (VATS) and mediastinoscopy will not be counted as major surgery and participants can be enrolled in the study  $\geq 1$  week after the procedure.
16. Participants (except those in Phase II Group 5) have not recovered from all toxicities related to prior anticancer therapies to grade  $\leq 1$  (CTCAE v 4.03). Participants in Phase II Group 5 will use version 5.0. Participants with any grade of alopecia are allowed to enter the study.
17. **Participants in Phase Ib and Phase II Groups 1 to 4** have out of range laboratory values defined as:
  - Absolute Neutrophil Count (ANC)  $< 1.5 \times 10^9/L$  ( $1.5 \times 10^3/\mu L$ )
  - Hemoglobin (Hgb)  $< 9$  g/dL (90 g/L)
  - Platelets (PLT)  $< 75 \times 10^9/L$  ( $75 \times 10^3/\mu L$ )
  - Total bilirubin  $> 1.5$  x upper limit of normal (ULN)
  - AST and/or ALT  $> 3$  x ULN, except for participants with liver metastasis who may not be included if AST and/or ALT  $> 5$  x ULN
  - Alkaline phosphatase (ALP)  $> 5$  xULN
  - Calculated creatinine clearance  $< 45$  mL/min (0.75 mL/sec) using Cockcroft-Gault formula
  - Asymptomatic serum amylase or lipase  $>$  Grade 2
  - Serum amylase or serum lipase CTCAE grade  $\geq 1$  with signs and/or symptoms suggesting pancreatitis or pancreatic injury (e.g. elevated P-amylase, abnormal imaging findings of pancreas, etc.)

Participants in Phase II Group 5 have out of range laboratory values defined as:

- Absolute Neutrophil Count (ANC)  $< 1.5 \times 10^9/L$  ( $1.5 \times 10^3/\mu L$ ) without growth factor support
- Hemoglobin (Hgb)  $< 9$  g/dL (90 g/L)
- Platelets (PLT)  $< 100 \times 10^9/L$  ( $100 \times 10^3/\mu L$ )
- Total bilirubin  $> 1.5$  x upper limit of normal (ULN)
- AST and/or ALT  $> 2.5$  x ULN except for participants with liver metastasis, who may not be included if AST and/or ALT  $> 5$  x ULN
- Alkaline phosphatase (ALP)  $> 5$  xULN

- Calculated creatinine clearance (using Cockcroft-Gault formula) < 50 mL/min
  - Asymptomatic serum amylase increase grade 1 and 2 are allowed if at the beginning of the study is confirmed to have no signs and/or symptoms suggesting pancreatitis or pancreatic injury (e.g., elevated P-amylase, abnormal imaging findings of pancreas, etc.)
  - Serum lipase > ULN
18. Participants have the following laboratory values outside of the laboratory normal limits or cannot be corrected to within normal limits with supplements during screening:
- Potassium
  - Magnesium
  - Phosphorus
  - Total calcium (corrected for serum albumin)
19. Participants receiving treatment with medications that are known to be:
- strong inhibitors or inducers of CYP3A4/5,
  - or CYP3A4/5, CYP1A2, CYP2C8, CYP2C9, CYP2C19, and/or CYP2D6 substrates with narrow therapeutic index,
  - or at risk for QT interval prolongation and/or Torsades de Pointe (long QT syndrome, family history of idiopathic sudden death or congenital long QT syndrome),
  - and cannot be discontinued or replaced by safe alternative medication within 5 half-lives or 7 days prior (whichever is longer) to the start of study treatment and for the duration of the study.
  - For Phase II Group 5 (capmatinib monotherapy): strong inducers of CYP3A that cannot be discontinued at least 1 week prior to the start of treatment with capmatinib and for the duration of the study.
  - Please refer to [Appendix 4](#) for a list of prohibited concomitant medications.
20. Participants who have impairment of GI function or GI disease that may significantly alter the absorption of study treatment (e.g., ulcerative diseases, uncontrolled nausea, vomiting, diarrhea, or malabsorption syndrome)
21. Pregnant or nursing (lactating) women.
22. Women of child-bearing potential, defined as all women physiologically capable of becoming pregnant, unless they are using highly effective methods of contraception during dosing and for 3 months after stopping the study treatments. Highly effective contraception methods include:
- Total abstinence (when this is in line with the preferred and usual lifestyle of the participant. Periodic abstinence (e.g., calendar, ovulation, symptothermal, post-ovulation methods) and withdrawal are not acceptable methods of contraception.
  - Female sterilization (have had surgical bilateral oophorectomy with or without hysterectomy), total hysterectomy, or bilateral tubal ligation at least six weeks before taking study treatment. In case of oophorectomy alone, only when the reproductive status of the woman has been confirmed by follow up hormone level assessment.
  - Male partner: male sterilization (at least 6 months prior to screening). For female participants on the study the vasectomized male partner should be the sole partner for that participant.

- Use of oral, injected or implanted hormonal methods of contraception or placement of an intrauterine device (IUD) or intrauterine system (IUS), or other forms of hormonal contraception that have comparable efficacy (failure rate <1%), for example hormone vaginal ring or transdermal hormone contraception.
  - In case of use of oral contraception women should have been stable on the same pill for a minimum of 3 months before taking study treatment.
  - Women are considered post-menopausal if they have had 12 months of natural (spontaneous) amenorrhea with an appropriate clinical profile (e.g. age appropriate, history of vasomotor symptoms). Women are considered not of childbearing potential if they are post-menopausal or have had surgical bilateral oophorectomy (with or without hysterectomy), total hysterectomy, or bilateral tubal ligation at least six weeks ago. In the case of oophorectomy alone, only when the reproductive status of the woman has been confirmed by follow up hormone level assessment is she considered not of childbearing potential.
23. Sexually active males unwilling to use a condom during intercourse while taking drug and for 3 months after stopping investigational medications. A condom is required for all sexually active male participants to prevent them from fathering a child AND to prevent delivery of study treatment via seminal fluid to their partner. In addition, male participants must not donate sperm for the time period specified above.
24. Participants with known hypersensitivity or contraindications to capmatinib or nazartinib, or any excipient of these agents.
25. For Group 5: Carcinomatous meningitis.
26. For Group 5: Known EGFR T790M positive, Known C797S positive, known druggable molecular alterations (such as ROS1, BRAF, KRAS etc.) who might be candidates for alternative targeted therapies as applicable per local regulations and treatment guidelines.
27. Participants who received live vaccines (e.g., intranasal influenza, measles, mumps, rubella, oral polio, BCG, yellow fever, varicella, TY21a typhoid vaccines and COVID-19 vaccines) within 30 days prior to the first dose of study treatment.

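### Exclusion criterion 19 lists long QT syndrome and family history under a medication-only stem, so as worded it excludes no one for these conditions

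*Protocol*

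**What the plan says.** Protocol Section 5.3, criterion 19, opens with the stem "Participants receiving treatment with medications that are known to be". The bullets beneath it cover strong CYP3A4/5 inhibitors or inducers, narrow-therapeutic-index substrates of several CYP enzymes, and then "at risk for QT interval prolongation and/or Torsades de Pointe (long QT syndrome, family history of idiopathic sudden death or congenital long QT syndrome". The next bullet adds the requirement that the item "cannot be discontinued or replaced by safe alternative medication within 5 half-lives or 7 days prior (whichever is longer) to the start of study treatment". A separate bullet for Group 5 monotherapy mentions only strong CYP3A inducers.

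Other criteria in the same section bear on QT risk:

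- Criterion 10 (uncontrolled cardiovascular disease) excludes a QTc of 470 "ms using Fridericia correction (QTcF) on the screening ECG (using the average QTcF of the triplicate ECGs" or higher. It also lists "Ventricular arrhythmias" and other arrhythmias not controlled with medication.
- Criterion 18 covers potassium, magnesium, phosphorus and calcium: "Participants have the following laboratory values outside of the laboratory normal limits or cannot be corrected to within normal limits with supplements during screening".
- Criterion 24 excludes "Participants with known hypersensitivity or contraindications to capmatinib or nazartinib, or any excipient of these agents".
- Criterion 5 lets the investigator exclude for a condition that, "in the judgment of the investigator, would make the participant inappropriate for the study".

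None of these names long QT syndrome or a family history. Nor do the key exclusions in the Protocol summary, which repeat the QTcF limit and refer to Section 5.3 for the full list.

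**The concern.** An exclusion criterion has to tell a site whom to turn away. Here the terms in the bracket describe patients and their relatives, while the grammar around them describes drugs. The Amendment 07 change list, used only as context, says criterion 19 was clarified for QT prolongation and Torsades de Pointe, so the bracket was presumably meant to do something.

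At stake is the entry of a participant with known hereditary QT risk, and consistency between sites. The protocol treats QT prolongation and Torsades as events to be managed on the combination and on each drug (Tables 6-7 to 6-9). Group 5 starts on capmatinib alone and may have nazartinib added at progression (Section 6.1.2). No endpoint, interim rule or sample size is affected.

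**Working it through.** The plan gives no figure to reproduce; the check is one of wording.

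**Step 1. Read criterion 19 as one sentence.**

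| Part | What it can describe |
|---|---|
| Stem | A medication the participant takes |
| Bullets 1 and 2 | Enzyme effect or substrate status of a medication |
| Bullet 3, before the bracket | Under the stem, a medication with QT or Torsades risk |
| Bullet 3, bracket | A diagnosis or a family history |
| Bullet 4 | Something that can be stopped or substituted, hence a medication |

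Take a participant with long QT syndrome on no listed drug: the stem is not met, so criterion 19 does not apply. Take the same participant on a QT-prolonging drug that cannot be replaced: criterion 19 applies because of the drug. In neither case does the bracket change the outcome.

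The bracket is unclear in one further way. Congenital long QT syndrome can be read as the participant's own diagnosis or as part of the family history.

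**Step 2. Look for the conditions elsewhere in Section 5.3.** There are 27 numbered criteria. One, criterion 19, names the conditions; 27 − 1 = 26 do not.

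**Step 3. Test each case against the other criteria.**

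| Case | Excluded by another criterion? |
|---|---|
| Long QT syndrome, screening QTcF ≥ 470 ms | Yes, criterion 10 |
| Long QT syndrome with a listed arrhythmia | Yes, criterion 10 |
| Listed electrolyte abnormal or not correctable | Yes, criterion 18 |
| Condition is a known contraindication to either drug | Yes, criterion 24 |
| Known long QT syndrome, QTcF < 470 ms, none of the above | Only if judged clinically significant, uncontrolled disease under criterion 10's open-ended list, or by judgement under criterion 5 |
| Family history alone, normal ECG | Only by judgement under criterion 5 |

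The last two rows are the gap.

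**Step 4. Whom it can reach.** The Amendment 07 rationale says Phase Ib and Groups 1 to 4 have met end-of-study criteria and no one in them is on treatment. Group 5 is planned at 10 + 20 = 30 (Section 4.1), with possible additions for discordant MET results. The protocol gives no frequency for the bracketed conditions, so no expected count can be formed.

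**The case against.** The strongest case against is that this is a drafting slip with little practical reach. Criterion 10 introduces its examples as a non-exhaustive list, so clinically significant, uncontrolled long QT syndrome could fall under it without being named. Criterion 5 gives any site that knows of such a condition an express ground to exclude. An investigator might also read the third bullet as meaning participants at risk and turn the patient away, so over-exclusion is as plausible as wrongful entry. All of this stands and limits the size of the point. It does not make the bracket work: the stem and the fourth bullet contradict the sympathetic reading, and discretion is what leads sites to differ.

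A reader might go further and infer that protection of such a participant rests on the entry criteria alone, because no QTc dose action is listed below 501 ms. Someone entering at just under 470 ms would then have 501 − 470 = 31 ms of rise before any action. The documents do not support that inference. The Grade 4 QTc rows in Tables 6-7, 6-8 and 6-9 also call for discontinuation on a change of more than 60 ms from baseline with Torsades, polymorphic ventricular tachycardia or signs of serious arrhythmia. Since 501 − 60 = 441, that rule can act below 501 ms for any baseline below 441 ms. The follow-up for QTcF prolongation (Section 6.3.4.1) and the ECG schedule (Section 7.2.2.6, Table 7-6) lie beyond the text available for this review, so nothing can be said about what they add. The 31 ms would in any case apply to every participant entering near the limit, not only to those with the named conditions.

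**Conclusion.** The point holds as a wording failure in an operative safety criterion. As written, criterion 19 excludes no one for long QT syndrome or for a family history of sudden death or long QT syndrome, and no other criterion in Section 5.3 names these conditions. The consequence is rare: mainly a participant with known long QT syndrome and screening QTcF below 470 ms, or one with a family history alone, in a group of about 30. Sites may decide such cases differently.

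This rests on a literal reading of the criterion and on Appendix 4, which was not available, being only what criterion 19 calls it: a list of prohibited medications. It assumes no prevalence and does not claim that any such participant has been enrolled. Whether family history alone ought to exclude is the sponsor's decision; the text does not settle it.

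**What to change.** In the next amendment:

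1. Limit the third bullet of criterion 19 to drugs with a known risk of QT prolongation and/or Torsades de Pointe, so that it fits the stem and the fourth bullet.
2. Put the participant condition on its own line, for example under criterion 10: *Long QT syndrome, including congenital, irrespective of co-medication*. State whether it applies to Group 5, because criterion 19's separate Group 5 bullet mentions only strong CYP3A inducers and leaves this open.
3. Decide whether a family history of idiopathic sudden death or congenital long QT syndrome excludes by itself. If so, list it on the new line; if not, delete it.

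The cost is one moved phrase, one history question at screening, and possibly a few participants who become ineligible. No analysis changes.
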